#### Drug exposure calculations

Drug eras will be defined as follows: Exposure starts at date of the first prescription after the first MDD diagnosis. For each prescription, the estimated duration of use is retrieved from the drug exposure table in the CDM. Subsequent prescriptions for the same drug will be combined into continuous exposed episodes (drug eras) using the following specifications:

Two drug eras will be merged into one continuous drug era if the distance in days between end of the first era and start of the second era is  $\leq 7$  days. The time between the two joined eras will be considered as exposed to the first era as show in in Figure 1.

	D2.2.3 –Study Protocol for P2 C1-008	
	Author(s): [name], [name]	Version: v3.1 – Final
	Dissemination level: public	

[figure not shown]

Gap era joint mode	Schematics	Dose in between	Cumulative dose	Cumulative time
“first”		$d_1$	$d_1 \cdot (x_1 + x_{12}) + d_2 \cdot x_2$	$x_1 + x_{12} + x_2$
“second”		$d_2$	$d_1 \cdot x_1 + d_2 \cdot (x_2 + x_{12})$	$x_1 + x_{12} + x_2$
“zero”		0	$d_1 \cdot x_1 + d_2 \cdot x_2$	$x_1 + x_{12} + x_2$
“join”		NA	$d_1 \cdot x_1 + d_2 \cdot x_2$	$x_1 + x_2$

[figure not shown]

**Figure 1. Gap era joint mode**

If two eras overlap, the overlap time will be considered exposed to the first era (Figure 2). No time will be added at the end of the combined drug era to account for the overlap.

If two eras start at the same date, the overlapping period will be considered exposed to both. We will not consider repetitive exposure.

[figure not shown]
Overlap mode	Schematics	Dose overlap
“first”		$d_1$
“second”		$d_2$
“both”		$d_1 + d_2$
“maximum”		$\max(d_1, d_2)$

**Figure 2. Gap era overlap mode**

To construct treatment pathways, various parameters can be defined in the TreatmentPatterns package (Figure 3). In this figure, an example medical file is presented, highlighting the key decisions required to formulate a treatment pathway for an individual undergoing treatments A, B, and C. For a comprehensive understanding of the parameters integrated into the treatment pathways, please refer to the table provided below for a detailed description:

	D2.2.3 –Study Protocol for P2 C1-008	
	Author(s): [name], [name]	Version: v3.1 – Final
	Dissemination level: public	

**Figure 3. Parameters in TreatmentPatterns package (25)**

The following parameters will be defined in this study.

Parameters	Values (days)	Description
periodPriorToIndex	0	Number of days prior to the index date of the target cohort
minEraDuration	0	Minimum time an event era should last to be included in analysis
eraCollapseSize	7	Window of time between which two eras of the same event cohort are collapsed into one era
combinationWindow	7	Window of time two event cohorts need to overlap to be considered a combination treatment
minPostCombinationDuration	7	Minimum time an event era before or after a generated combination treatment should last to be included in analysis
filterTreatments	All	Select all treatments including first time occurrences and sequential repeated treatments
maxPathLength	5	Maximum number of steps included in treatment pathway

For all continuous variables, summary descriptive statistics will be reported: median and interquartile interval will be reported. For all categorical analyses, counts and percentages will be reported. A minimum cell count of 5 will be used when reporting results, with any smaller counts reported as “<5”. All analyses will be

	D2.2.3 –Study Protocol for P2 C1-008	
	Author(s): [name], [name]	Version: v3.1 – Final
		Dissemination level: public

reported by country/database, overall and stratified by age and sex when possible (minimum cell count reached).

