#### Rationale and Background

In clinical trials involving patients with major depressive disorder, participants who start treatment may experience *intercurrent events* (IEs) during follow-up, such as treatment discontinuation, switch to alternative therapies, or changes in background/concomitant therapies (e.g., sleep aids). The ICH E9(R1) guideline defines IEs as events that occur after treatment initiation and influence the interpretation of the outcome of interest or after which the outcome no longer exists (e.g., death).

While target estimands in these trials may adopt a treatment policy or composite strategy to handle these IEs, it is crucial to recognize that the rate at which these intercurrent events occur significantly impacts the interpretation of estimated treatment effects.

To gain a more comprehensive understanding of the external validity of clinical trials in this indication, it is essential to assess whether the rate of occurrence of these IEs is similar in real-life settings compared to what is observed in the clinical trials. By obtaining such insights, the results of this study aim to provide valuable information regarding the generalisability of clinical trial findings to real-world scenarios.

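### The five-step pathway cap, with every repeated era kept, can bind before week 24 and may distort treatment status and late switches or stops in the tabulated proportions

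*Protocol*

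**What the plan says.** The parameter table under Figure 3 in Section 8.8.3 fixes the settings that matter here:

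- maxPathLength = 5: "Maximum number of steps included in treatment pathway". The column is headed in days, but this entry is a count of steps.
- filterTreatments = All: "Select all treatments including first time occurrences and sequential repeated treatments".
- eraCollapseSize = 7: "Window of time between which two eras of the same event cohort are collapsed into one era". The drug-era text of the same section sets the same 7-day limit.
- minEraDuration = 0: "Minimum time an event era should last to be included in analysis". No short era is dropped.
- combinationWindow = 7 ("Window of time two event cohorts need to overlap to be considered a combination treatment") and minPostCombinationDuration = 7 ("Minimum time an event era before or after a generated combination treatment should last to be included in analysis").

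The Abstract (Data analyses) assigns the Objective 1 and 3 results, tables as well as plots, to TreatmentPatterns. Section 8.8.3 takes the switching and discontinuation criteria from that package. It also asks for the percentage of patients on each listed treatment at index and at 4, 6, 8, 12 and 24 weeks. Table 9 makes initiation, switching and discontinuation binary per patient.

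The text under Figure 1 says that repeat exposure will be left out of account. That sits uneasily with filterTreatments = All.

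**The concern.** Each new era after a gap of more than 7 days is a further step, and so is each addition or removal of a second class. Intermittent use therefore consumes steps quickly. The Rationale names "changes in background/concomitant therapies (e.g., sleep aids" among the events of interest, and sleep aids are drugs that may be taken on and off.

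No second, uncapped counting route is described. Sections 8.8.4 and 11 say that the loss-to-follow-up sensitivity analysis is run overall only because the package cannot produce it, which implies that the stratified main results do come from the package. If the week 4 to 24 tables are read from the capped path, whatever follows step five is absent, and increasingly so at later windows. The study is meant to set event rates in practice beside those in trials, so an error that grows with follow-up matters. Nothing planned would reveal it: Section 11 reports only how many patients have enough follow-up at each interval.

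**Working it through.** The protocol states no truncation rate, so there is no figure to reproduce. The check is a step count.

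**Inputs from the protocol:** cap of 5 steps; repeats kept; eras of one class stay separate when the gap is 8 days or more; no minimum era length; windows at days 28, 42, 56, 84 and 168.

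**Assumed inputs:** era length d, gap g, and days s from antidepressant start to first psycholeptic. The only supply figure in the protocol is an antidepressant example of 30 daily pills (Section 11). The values s = 7 and g = 8 just satisfy the 7-day combination parameters.

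**First day of step 6, the first step cut:**

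- One class pathed alone: 5(d + g), counted from its first era.
- Shared path, continuous antidepressant, psycholeptic added on day s: s + 2(d + g).
- Shared path, both started the same day: 3d + 2g.

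| Layout | d on / g off | Step 6 starts | By day 168? |
|---|---|---|---|
| One class | 7/8 | 5 × 15 = day 75 | yes |
| One class | 14/8 | 5 × 22 = day 110 | yes |
| One class | 25/8 | 5 × 33 = day 165 | yes |
| One class | 28/8 | 5 × 36 = day 180 | no |
| One class | 30/8 | 5 × 38 = day 190 | no |
| One class | 14/14 | 5 × 28 = day 140 | yes |
| One class | 21/14 | 5 × 35 = day 175 | no |
| One class | 7/30 | 5 × 37 = day 185 | no |
| Shared, s = 7 | 14/8 | 7 + 2 × 22 = day 51 | yes |
| Shared, s = 7 | 28/8 | 7 + 2 × 36 = day 79 | yes |
| Shared, s = 7 | 30/8 | 7 + 2 × 38 = day 83 | yes |
| Shared, s = 28 | 30/8 | 28 + 2 × 38 = day 104 | yes |
| Shared, s = 7 | 60/8 | 7 + 2 × 68 = day 143 | yes |
| Shared, s = 7 | 60/30 | 7 + 2 × 90 = day 187 | no |
| Same-day start | 30/8 | 90 + 16 = day 106 | yes |
| Same-day start | 51/8 | 153 + 16 = day 169 | no |

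One class alone cannot reach step 6 by week 4 or week 6: even 1-day eras with 8-day gaps give 5 × 9 = day 45.

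**What is lost.** Take the shared path with s = 7 and 30/8. Steps start on days 0, 7, 37, 45, 75, 83, 113, 121, 151 and 159, which is ten steps by day 168.

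- First psycholeptic initiation is step 2 and its first stop is the end of step 2. Both survive the cap.
- The capped path ends with antidepressant alone, on day 83. The full path is on antidepressant plus psycholeptic at week 12 (day 84) and at week 24 (day 168), so status is wrong at both.
- A first antidepressant switch or stop after day 83 lies beyond the fifth step. It would be missed, or the antidepressant would appear to end on day 83.

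**A cap that cannot bind.** For one class with 1-day eras and 8-day gaps, steps start every 9 days: 168/9 = 18.7, so 19 steps start by day 168 (days 0 to 162). A cap sized on 7-day eras (168/15 = 11.2, so 12 steps) could still bind, because minEraDuration is 0. On a shared path each psycholeptic era adds about two steps, hence about double.

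**The case against.** Three objections have force.

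*The cap may not touch the tables.* The text limits steps in a treatment pathway. It does not say that the proportions are counted from the truncated path, and how the package applies the cap is not in the document. An analysis plan not at hand may settle it. This stands: the loss is conditional. But every indication in the protocol points to the package output, and no other route is given.

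*Overrun depends on chosen inputs.* A reader might infer that intermittent psycholeptic use necessarily overruns five steps. The document does not support that. It gives no psycholeptic era or gap length, an 8-day gap is the shortest that escapes the collapse rule, and single-class eras of 28 to 30 days fit. A shared path is not stated either. Section 8.6.2 compiles one treatment list covering antidepressants and psycholeptics, and Table 2 merges both in one objective. Against that, the Abstract times psycholeptic switching and stopping from psycholeptic start, which is compatible with a separate path.

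*The outcomes are binary first events.* A reader might infer that the initiation and discontinuation proportions for psycholeptics are broadly biased. They are not: in the modelled paths both first events fall in step 1 or 2. A hypnotic user who looks stopped at week 24 already had a gap of more than 7 days much earlier. This objection does not cover the percentages on treatment at fixed weeks (Section 8.8.3), or a first switch or antidepressant stop that comes late.

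**Conclusion.** The point holds in a limited form. The stated settings allow a path to exceed five steps before day 168. On a shared path this happens readily: step 6 starts between days 51 and 143 for psycholeptic eras of 14 to 60 days, with s = 7 and 8-day gaps. On a single-class path it needs eras of 25 days or less at the shortest gap. If the tables are read from the capped path, treatment status at weeks 12 and 24 and late first switches or antidepressant stops can be lost or misdated, while first psycholeptic initiation and first stop are largely safe. The share of patients affected cannot be estimated from the document. The conclusion rests on assumed era and gap lengths, on the path layout, and on the tables being taken from the capped path. Severity is low to moderate.

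**What to change.** 1. Compute the week 4 to 24 tabulated proportions without the cap, and say so in Section 8.8.3. Alternatively, set maxPathLength high enough that no path reaches it by day 168: at least 19 for a single class, given 1-day eras and 8-day gaps, and about double on a shared path. Counting without the cap is cleaner, because several alternating classes could need more steps still.
2. Keep 5 for the sunburst and Sankey plots only.
3. Report, for each window, the number of paths that reach the cap.
4. State whether antidepressants and psycholeptics share one path.
5. Reconcile filterTreatments = All with the statement under Figure 1 that repeat exposure is left out of account, or limit that statement to the drug-era calculation if that is its scope.

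The cost is one parameter value, one extra count and a few sentences. Longer paths produce more rare sequences, so more cells below 5 would be masked in the path listing.

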#### 8.8.4 Sensitivity analysis

If the percentage of people who dropped from the analysis at week 24 is high (where high is defined as more than 50% of individuals participating at week 4 do not longer participate at week 24), we will do a sensitivity analysis where i) we assume that the people who were lost for follow-up continued treatment and ii) and assume that people who were lost to follow-up discontinued treatment. As this analysis can not be generated by the treatment pattern package, we will only do this for the overall analysis (thus not stratified by age and sex). (see also section on limitation)

	D2.2.3 –Study Protocol for P2 C1-008	
	Author(s): [name], [name]	Version: v3.1 – Final
		Dissemination level: public

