### Data analyses

Objective 1: The number and percentage of patients with newly diagnosed MDD initiating treatment with antidepressants will be estimated at 4, 6, 8, 12, and 24 weeks after date of new MDD diagnosis; and the number and percentage of those discontinuing and switching treatment at 4, 6, 8, 12, and 24 weeks following start of antidepressant therapy. They will be reported in tabular form as absolute numbers as well as

	D2.2.3 –Study Protocol for P2 C1-008	
	Author(s): [name], [name]	Version: v3.1 – Final
		Dissemination level: public

proportions, and depicted using Sunburst plots and Sankey diagrams. The statistical analyses will be performed based on OMOP-CDM mapped data using the “TreatmentPatterns” R package.

Objective 2: The duration (mean, median, quantiles 25% and 75%, minimum and maximum) of antidepressant use in patients with newly diagnosed MDD during the first treatment era will be estimated. The index date will be determined as the date of the first prescription of the specific antidepressant class for each individual. Statistical analyses will be conducted using the "DrugUtilization" R package based on OMOP-CDM mapped data.

Objective 3: The number and percentage of patients with newly diagnosed MDD initiating, switching, or discontinuing treatment with psycholeptics) will be estimated at 4, 6, 8, 12, and 24 weeks after the date of treatment initiation with antidepressants; and at 4, 6, 8, 12, and 24 weeks after starting psycholeptics (for switching or discontinuing treatment). This will be reported in tabular form as absolute numbers as well as proportions and depicted using Sunburst plots and Sankey diagrams. The statistical analyses will be performed based on OMOP-CDM mapped data using the “TreatmentPatterns” R package.

For all analyses, results will be reported with a minimum cell count of 5, and any counts smaller than 5 will be reported as <5 to ensure privacy and confidentiality.

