For the treatment pattern analysis, we will look at specific time intervals following treatment initiation namely at week 4, 6, 8, 12 and 24 following treatment initiation. Only patients with sufficient follow-up at these intervals will be included for this analysis, implying that patients for instance which were initially included for the analysis at week 4 might not longer be included at week 6 because of lost to follow-up. As part of the results, we will provide the number of individuals included in the analysis at the different time intervals which will provide information on the extent of people who dropped out from the analysis. If the percentage of people who dropped from the analysis at week 24 is high (where high is defined as more than 50% of individuals participating at week 4 do not longer participate at week 24), we will do a sensitivity analysis where i) we assume that the people who were lost for follow-up continued treatment and ii) we assume that the people who were lost to follow-up discontinued treatment. As this analysis can not be generated by the treatment pattern package, we will only do this for the overall analysis (thus not stratified by age and sex).

The number of pills (per package) of the antidepressant of interest might vary by countries which might bias the proportion of individuals continuing treatment. Indeed, if the antidepressant is dosed as one pill daily, and the initial prescription is a package of 30 pills, by definition the patient will be considered as having continued treatment at week 4 even if the patient discontinued treatment in the meantime. To contextualize this potential misclassification, we will provide information on the median quantity (with min, max, P25 and P75) by type of antidepressant and by database.

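### The package limit does not justify keeping the loss-to-follow-up scenarios out of the age and sex strata

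*Protocol*

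**What the plan says.** Under section 11, the treatment-pattern analysis at weeks 4, 6, 8, 12 and 24 includes only patients with enough follow-up at each interval. Section 8.8.4, repeated in section 11, adds a conditional sensitivity analysis for when drop-out is high, "where high is defined as more than 50% of individuals participating at week 4 do not longer participate at week 24". There are two scenarios: "i) we assume that the people who were lost for follow-up continued treatment", and the opposite, to "assume that people who were lost to follow-up discontinued treatment".

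Both sections then limit its scope: "we will only do this for the overall analysis (thus not stratified by age and sex". The ground stated for this limit is one of software: "As this analysis can not be generated by the treatment pattern package". No other reason is given.

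Elsewhere the protocol commits to these outputs:
- The abstract (Data analyses, Objective 1) plans "the number and percentage of those discontinuing and switching treatment at 4, 6, 8, 12, and 24 weeks following start of antidepressant therapy".
- Section 8.8.3 promises counts and percentages for categorical results, with all analyses "reported by country/database, overall and stratified by age and sex when possible (minimum cell count reached".
- Section 11 states that "we will provide the number of individuals included in the analysis at the different time intervals".

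**The concern.** The reason given does not separate what is kept from what is dropped. If the package cannot generate the scenarios, it cannot generate the overall version either. The study team has therefore already accepted computing them outside the package, and the same calculation works within a stratum.

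Objectives 1 and 3 are to be reported by age group and sex. Each stratified discontinuation proportion is a figure among patients still followed, so it depends on who has left. Nothing in the protocol suggests that loss is the same at ages 12-17 as at 65 and above. With the analysis confined to the overall population, the 50% criterion is in effect read there too. A stratum can then lose most of its patients and still be reported with no indication of how far that loss could move its estimate.

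**Working it through.** The protocol gives no computed figure to reproduce here, since 50% is a chosen threshold. It gives no loss or discontinuation rates either, so every rate below is an assumption.

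**What the scenarios need.** For one stratum in one database:
- W: participants at week 4, the base used in the 50% criterion.
- n: those still in the analysis at week t (numbers per interval, section 11).
- d: those among n who have discontinued (abstract; section 8.8.3).

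Scenario (i), all lost continued: d/W.

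Scenario (ii), all lost discontinued: (d + W - n)/W.

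The difference is (W - n)/W, which is the fraction lost. Both scenarios as written can therefore be computed from three counts, in a stratum as well as overall.

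**Size of the gap between scenarios.** Take W = 1,000 and assume that 40% of those still followed have discontinued:

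| Loss by week 24 | n | d | Scenario (i) | Scenario (ii) |
|---|---|---|---|---|
| 30% | 700 | 280 | 28.0% | 58.0% |
| 45% | 550 | 220 | 22.0% | 67.0% |
| 49% | 510 | 204 | 20.4% | 69.4% |
| 70% | 300 | 120 | 12.0% | 82.0% |

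**What an overall trigger can miss.** Let one stratum hold 10% of patients and lose 70%, and let the other 90% lose 47.2%:

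0.10 × 0.70 + 0.90 × 0.472 = 0.0700 + 0.4248 = 0.4948, or 49.5%.

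This is below 50%, so nothing is triggered, although in that stratum the scenarios are 70 points apart.

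**A second assumed example.** Take four age groups of 2,000, 40,000, 35,000 and 23,000 patients, with assumed loss of 70%, 60%, 45% and 30%. Expected overall loss is (1,400 + 24,000 + 15,750 + 6,900)/100,000 = 48.05%, and a simulation on these inputs gave 48.2%. The trigger is again not reached, although two of the four groups are above 50%. The scenarios from counts alone equalled those from simulated patient records in every group, as the algebra requires. For example, they were 16.3% and 86.7% at ages 12-17.

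**What the counts cannot do.** If patients seen to discontinue before being lost keep that status, scenario (i) rises. When half of the lost discontinuers were assumed to have been seen discontinuing, the scenario (i) values of 16-28% across the four groups became 34-36%. That version needs a cross-tabulation made locally at each database. Scenario (ii) is unchanged.

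**The case against.** The restriction is stated openly, with a reason, for a conditional sensitivity analysis in a descriptive study without hypotheses. It alters no main estimate. If the stratum counts are published, a reader can do the arithmetic from the report, the dashboard or the aggregated data offered in section 14.1.

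Heavy loss may also be uncommon. Section 8.2 gives a mean follow-up of 15 years for SIDIAP, a median of 4.7 years for IPCI and an average of 6.37 years for IMASIS. In IQVIA DA Germany, where observation ends at the last consultation, loss could be high overall and would then trigger the analysis anyway.

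Much of this limits the importance of the point, but it does not rescue the reason given. The follow-up figures are whole-database averages and do not rule out heavy loss in one stratum. Leaving the calculation to the reader depends on the interval numbers being shown by stratum. The section 11 sentence does not say so; it has to be inferred from the general statement in section 8.8.3.

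A reader might go further and infer that high-loss strata are left with no information at all, or that the 50% condition should be dropped. The documents do not support either. Section 11 reports interval numbers precisely to show the extent of drop-out. Whether to have a threshold is a design preference: without one, 6 drug classes × 5 time points × 6 age or sex strata × 5 databases gives 900 pairs for discontinuation alone.

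**Conclusion.** The point holds as a modest weakness. The stated reason does not justify excluding age and sex strata, and an overall-only trigger can miss a stratum that loses well over half its patients. How far apart the scenarios lie equals the fraction lost, whatever the discontinuation rate. The 10% stratum, the 70% and 47.2% losses and the 40% discontinuation are assumptions, and the documents do not show that any stratum will reach such loss.

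Two other readings should be avoided:
- d/W is not a strict lower bound. It is the literal form of scenario (i), and it counts as continuing anyone who was seen to stop and then left the data.
- Not every stratified result is affected. The scenarios concern discontinuation proportions. Objective 2 is a summary of duration, and section 8.8.4 defines no scenario for switching.

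The availability of stratum counts rests on section 8.8.3 and is subject to the masking of counts below 5 (section 8.8.2).

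**What to change.** In sections 8.8.4 and 11:
1. Delete the restriction to the overall analysis.
2. State that the numbers in the analysis at each interval are reported by age group and sex as well as overall.
3. Check the 50% criterion within each database and each age and sex stratum.
4. Where it is met and cells are not masked, report both discontinuation scenarios for that stratum as d/W and (d + W - n)/W. State that the base is week-4 participants, to match the criterion; losses before week 4 then stay outside the scenarios.
5. State that patients seen to discontinue before being lost keep that status if a local cross-tabulation is available. Otherwise label scenario (i) as the literal assumption.
6. State that the scenarios do not cover duration or switching.

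The cost is a few sentences, a little more analysis outside the package and a longer annex table. The count-based version needs no new data extraction; the optional cross-tabulation in step 5 needs one further local output.
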